7.8.2. Variable Identification for Propensity Score Model

7.8.2.1. Variable Identification Based on Literature, Previous Work, and Clinical HCP Input

Prior to the initiation of data collection, a comprehensive literature review was conducted to identify the risk factors or covariates associated with bleeding events among PwSHA. No real world data is currently published on characteristics associated with usage of gene therapy compared to other hemostatic therapies. The findings from this review identified a list of potential variables to be assessed in the PS. The comprehensive literature review was designed to capture the most relevant

and high-quality studies based on a fit-for-purpose search strategy developed using key words, medical subject heading (MeSH) terms, and Boolean operators. There were no date or geographic restrictions for the search, but only articles published in English were included. In addition, meeting abstracts were also excluded. After a comprehensive search strategy was developed, the search was executed on November 21, 2023 across the following online databases: Embase, OVID Medline, and the Cochrane Library (CDSR/CENTRAL).

Utilizing the Population, Intervention, Control, Outcome, and Study Design (PICOS) framework, fit-for-purpose study selection criteria was developed. Study selection was conducted in two phases, title/abstract screening, and full-text screening. The initial title and abstract screening was completed by one reviewer (using a conservative approach – including articles that might have missing/unsure PICOS criteria), while subsequent full-text screening was completed by two independent reviewers, where conflicts were resolved between the two reviewers. In addition to the PICOS criteria, only articles that examined the association between HA treatment and bleeding events while considering covariates, either as part of the study design (i.e., pre-randomization stratification or matching) or adjustments in the analysis, were included.

A data extraction form was created, and pilot tested including information on study characteristics, participant characteristics/study population, analysis details, and covariates considered in the study design or analysis of included studies. Once the data extraction form was pilot tested, the first reviewer extracted data based on the presented columns, while the second reviewer verified all the extracted data for quality assurance purposes. After completion of the data extraction, a qualitative synthesis of the included articles was conducted to summarize the articles included in the literature review and to recommend a list of covariates to include in the PS. Overall, the comprehensive literature review included 14 unique studies for covariate assessment (see the protocol for an overview of the literature review results). After HCP expert review, one additional study³¹ was also considered to provide recommendations for covariates to include in the PS in order to compliment the results from the comprehensive literature review. This study used predictive modeling to identify predictors of long-term ABR during prophylaxis with EHL FVIII.

In addition to the comprehensive literature review results, HCP expert advice and previous work on developing PS for the comparison of Roctavian to FVIII prophylaxis (as part of the Roctavian clinical development²⁹) has informed/confirmed the list of potential variables to assess for inclusion in the PS. In particular, HCPs in Germany treating PwSHA with either Roctavian or SoC products advised the study team regarding overall study conduct and interpretation, as well as providing input into variables identified for PS inclusion. HCPs provided input into variables both associated with the endpoint of bleeding events as well as factors associated with choosing Roctavian treatment.

Table 6 outlines the potential variables to include in the PS based on the comprehensive literature review, expert physician input, and prior comparative Roctavian versus FVIII prophylaxis studies PS development along with considerations for inclusion based on clinical relevance, potential statistical associations, and anticipated correlations between variables. Prior bleeding history, ABR (12 months prior to index date), will be included in the PS regardless of statistical significance due to clinical significance based on feedback from German physicians.

Table 6: List of Potential Variables for Inclusion in PS

Variable	Found by literature review	From previous PS work	Clinical expert opinion	Considerations
Baseline/prior bleeding history (e.g., ABR)	✓	✓	✓	Include regardless of statistical association, based on clinical relevance
Baseline FVIII utilization	✓	✓	✓	Include based on statistical association and correlation with other variables (e.g., baseline/prior bleeding history and baseline prophylaxis class)
Baseline prophylaxis class (FVIII vs. emicizumab)	✓	✓	✓	Include based on statistical association and correlation with other variables (e.g., baseline/prior bleeding history and FVIII utilization)
Age	✓	✓	✓	Include based on statistical association
Height, Weight and/or BMI	✓	✓	✓	Include based on statistical association
Baseline von Willebrand factor (IU/mL)	✓	X	✓	Include based on statistical association
Number of target joints	✓	✓	X	To be considered depending on statistical association and correlation with other variables (e.g., baseline/prior bleeding history and joint health score)
Joint health (e.g., baseline/prior HJHS)	X	X	✓	To be considered depending on statistical association and correlation with other variables (e.g., baseline/prior bleeding history and number of target joints)
Baseline/prior type of bleeds	X	X	✓	To be considered depending on statistical association and correlation with other variables (e.g., baseline/prior bleeding history and target joints)
Geography (HTC/site/region/country)	✓	✓	X	Site to be considered depending on statistical association and correlation with other variables
Prophylaxis class switching (e.g., SHL/PD to EHL/emicizumab)	✓	✓	X	To be considered depending on statistical association and correlation with other variables
Baseline/prior pain (e.g., BPI-sf)	X	X	✓	To be considered depending on statistical association and correlation with other variables (e.g., target joints and HJHS)

Variable	Found by literature review	From previous PS work	Clinical expert opinion	Considerations
Baseline/prior QoL (e.g., haemo-QoL-A)	X	X	✓	To be considered depending on statistical association and correlation with other variables
Activity status	X	X	✓	Not considered as this there is no validated questionnaire for lifestyle factors in PwSHA
Baseline/prior history of liver fibrosis/cirrhosis	✓	X	X	Significant liver fibrosis/cirrhosis is accounted for by the exclusion criteria, but less severe liver fibrosis to be considered based on statistical association
Baseline/prior history of hepatitis B and C	✓	X	X	Not considered as this is accounted for by study exclusion criteria
Baseline/prior history of HIV positivity	✓	X	X	Include based on statistical association
Baseline/prior history of cancer	✓	X	X	Include based on statistical association
Baseline/prior history of hypertension	✓	X	X	Include based on statistical association
Baseline/prior history of osteoporosis	✓	X	X	Include based on statistical association
Adherence to treatment	✓	X	X	Not considered as there is not enough prior literature/evidence to suggest as factor related to bleeding outcomes; confirmed by clinical expert
Genotype	X	X	X	Not considered as this is a factor for inhibitor development but not bleeding outcomes and accounted for by study exclusion criteria for history of or current inhibitors

Abbreviations: ABR: annualized bleeding rate; BMI: body mass index; EHL: extended half-life; FVIII: coagulation factor VIII; HIV: human immunodeficiency virus; HTC: hemophilia treatment center; PD: plasma-derived; PwSHA: people with severe hemophilia A; QoL: quality of life; SHL: standard half-life.

Note: Other variables identified in the literature review but not outlined in Table 6, due to lack of relevance to this study and the association comparing Roctavian and SoC and bleeding outcomes were ethnicity, treatment duration, pharmacokinetic (PK)-guided dosing use, prophylaxis vs on-demand treatment, concurrent medications (bypass agents, non-steroid anti-inflammatory drugs, tranexamic acid, and corticosteroid), and hemophilia severity.

7.8.2.2. Exploration of Unmeasured Confounding

As it may not be feasible to collect all potential variables associated with treatment choice or bleeding outcomes (such as individual lifestyle choices) due to the nature of the study and maximizing data quality for the study when working with an existing registry, it is possible that residual confounding exists as a result of unobserved variables not included in the PS, which could influence the direction and/or magnitude of results observed. Therefore, the E-value, as reported by VanderWeele and Ding, will be used to explore this further.³²

The E-value is the minimum strength of association, on the risk ratio scale, that an unmeasured confounder would need to have with both the treatment and outcome, conditional on the measured covariates, to explain away a treatment–outcome association. The E-value focuses on the magnitude of the confounder associations that could produce confounding bias equal to the observed treatment–outcome association.

E-value calculations are straightforward. For an observed risk ratio of RR:

$$\text{E-value} = \text{RR} + \sqrt{\text{RR} \times (\text{RR} - 1)}$$

The formula applies to a risk ratio greater than 1; for a risk ratio less than 1, one first takes the inverse of the observed risk ratio and then applies the formula.

The interpretation of the E-value along with a qualitative assessment, including clinical input from health care practitioners in Germany, will be incorporated into the interpretation of results.

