7.6. Study Sample Size

The primary goal of HA treatment is to reduce the bleeding rate or to achieve freedom from bleeding. As an approximation of the appropriate number of cases for the data collection accompanying the application, the Institute for Quality and Efficiency in Health Care (IQWiG) conducted the sample size calculation based on ABR for treated bleeds. Evaluation of the ABR is performed using a negative binomial model.

The formula for The sample size calculation is as follows:

$$N_1 \geq \frac{(z_\alpha \sqrt{V_0} + z_\beta \sqrt{V_1})^2}{(\log(R_0) - \log(\lambda_2/\lambda_1))^2}$$

$$N_2 = \theta N_1$$

Where:

$$V_1 = \frac{1}{\mu_t} \left(\frac{1}{\lambda_1} + \frac{1}{\theta \lambda_2} \right) + \frac{(1 + \theta)\varphi}{\theta}$$

V_0 is computed using the fixed marginal total method, the 2nd method recommended by Zhu et al.:²⁷

$$V_{02} = \frac{(1 + R_0\theta)^2}{\mu_t R_0 \theta (\lambda_1 + \theta \lambda_2)} + \frac{(1 + \theta)\varphi}{\theta}$$

N_1 is the sample size for control, N_2 is the sample size for intervention. $\theta = \frac{N_2}{N_1}$, which is the sample size ratio; R_0 is the superiority margin ratio at the null hypothesis. In this case, R_0 is <1 since higher rates are worse. λ_1 is the event rate in the control group, and λ_2 is the event rate in the intervention group. φ is the dispersion parameter, and μ_t is the average exposure time. z_α is the z-score at the significance level, z_β is the z-score at the power value.

When higher rates are worse, the superiority by a margin test hypotheses are

$$H_0: \frac{\lambda_2}{\lambda_1} \geq R_0 \quad \text{vs.} \quad H_1: \frac{\lambda_2}{\lambda_1} < R_0$$

Where $R_0 < 1$.

The relative effect measure is the incidence rate ratio of Roctavian over SoC, which can be tested against the shifted null hypothesis of 0.5, assuming a significance level $\alpha = 2.5\%$ with a one-sided test, and power of at least 80%. Higher values for the ABR (parameter λ) stand for a worse outcome. Furthermore, a distribution of the Sample Roctavian vs. SoC of 1:5 is assumed (sample size ratio $\theta = 0.2$). Other required parameters are the Average Exposure Time ($u_t = 1$ year), the ABR for the SoC and Roctavian groups ($\lambda_{SoC} = 3$, $\lambda_{Roctavian} = 0.85$) and a value for the overdispersion ($\phi = 1.5$). This results in a total sample size of at least 397 participants (Roctavian Cohort $n = 67$, control Cohort $n = 330$).

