more similar Roctavian and SoC Cohorts. Other clinically significant prognostic factors or covariates that remain imbalanced after propensity score adjustment will be included in the model as well. Regression coefficients, corresponding 95% CIs and p-values will be reported for all explanatory variables included in the model. The estimated rate ratio (ABR in Roctavian Cohort / ABR in SoC Cohort) generated from the IPTW weighted negative binomial model will be tested against the shifted null hypothesis of 0.5. For an alpha=0.025 test, the shifted null hypothesis is rejected if the upper boundary of the two-sided 95% CI for the rate ratio is less than the null hypothesis 0.5. The CI of the estimated rate ratio will be calculated using the Wald method.²⁷

Given some participants may have no treated bleeds based on prior literature,⁴⁶ a two-part zero-inflated negative binomial model will also be considered. If the negative binomial model does not converge,⁴⁷ or if the AIC in the model accounting for zero-inflation is lower, then the zero-inflation negative binomial model will become the primary objective analytic model, as lower AIC indicates a better fit. For the zero-inflated negative binomial model, first the model will be fit for a binary outcome whether a participant had a treated bleed during the outcome assessment period, and then an ABR count outcome for treated bleeds among participants who had at least one treated bleed during the outcome assessment period (excluding participants with zero bleeds) will be fit. Finally, the unconditional ABR estimates for treated bleed will be calculated by multiplying the estimated conditional ABR from the count model by the probability of having a treated bleed estimated from the binary model for both the Roctavian and SoC Cohorts.

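### The planned E-value uses only the point estimate against a ratio of 1: it ignores sampling uncertainty and does not address the SAP's test against 0.5

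*Protocol*

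**What the plan says.** Protocol 10.3.4 and SAP 7.8.2.2 carry the same text. The E-value is the strength of association an unmeasured confounder would need with both treatment and outcome "to explain away a treatment–outcome association". The formula is introduced with "For an observed risk ratio of RR", and "for a risk ratio less than 1, one first takes the inverse of the observed risk ratio and then applies the formula". The reference is therefore 1 and the input is the point estimate. Neither section mentions a confidence limit or another reference value. The result is to be read with a qualitative clinical assessment when the findings are interpreted.

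SAP 7.9.3 sets the primary decision. The weighted negative binomial rate ratio "will be tested against the shifted null hypothesis of 0.5". At a one-sided alpha of 0.025, success requires the upper 95% limit for that ratio to fall below the margin. SAP 7.6 sizes the study for the same hypothesis "with a one-sided test, and power of at least 80" per cent.

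The protocol differs on both the null and the measure. Section 10.1 uses the 0.5 margin for sample size only and says the hypotheses actually tested are not shifted. Section 10.3.6.1 makes the difference in mean ABR, by a two-sample t-test, the primary comparison.

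**The concern.** An E-value supports a conclusion only if it is computed for the quantity on which that conclusion rests. Here the planned figure has two gaps.

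- **No sampling uncertainty.** A point estimate far from 1 gives a large E-value even when the interval reaches much closer to 1.
- **No link to the 0.5 rule.** Under SAP 7.9.3, success fails once the upper limit reaches 0.5. Much less confounding is needed for that than to move the estimate to 1.

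The study is not randomised. The documents accept that lifestyle and individual experience of the disease will go unmeasured, and the E-value is the only method they specify for judging how strong such confounding would have to be. Of the four values obtained by crossing estimate or limit with reference 1 or 0.5, the planned one is always the largest for a result that meets the SAP rule. The protocol's difference in mean ABR also supplies no ratio for the formula, so the text should say which estimate is entered.

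**Working it through.** **Inputs (SAP 7.6).** Rates 3 (SoC) and 0.85 (Roctavian) per year, dispersion 1.5, exposure 1 year, allocation ratio 0.2, margin 0.5, one-sided alpha 0.025, power 80%, groups of 330 and 67. The 3-year case takes the planned follow-up per participant as exposure.

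**The plan's own figure.** The printed formula gives V0 = 12.82 and V1 = 15.22, hence 328.8 SoC and 65.8 Roctavian participants. Rounded up, this is 329 + 66 = 395, against 397 stated. Power at 330 and 67 is 80.6%. The design inputs are therefore understood correctly.

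**E-value function.** E(x) = x + √(x(x − 1)) for x > 1.

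**Design ratio.** RR = 0.85/3 = 0.2833.

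- Planned value: x = 1/0.2833 = 3.529, so E = 3.529 + √(3.529 × 2.529) = 6.52.
- Estimate against 0.5: x = 0.5/0.2833 = 1.765, so E = 1.765 + √(1.765 × 0.765) = 2.93.

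**Expected upper limit.** SE(log RR) = √[(1/(0.85t) + 1.5)/67 + (1/(3t) + 1.5)/330], with t the exposure in years.

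- t = 1: SE = 0.213; limit = 0.2833 × exp(1.96 × 0.213) = 0.430.
- t = 3: SE = 0.182; limit = 0.2833 × exp(1.96 × 0.182) = 0.405.

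| E-value for | 1 year | 3 years | Planned 6.52 is larger by a factor of |
|---|---|---|---|
| Upper limit against 1 | 4.08 | 4.38 | 1.6 / 1.5 |
| Estimate against 0.5 | 2.93 | 2.93 | 2.2 |
| Upper limit against 0.5 | 1.60 | 1.77 | 4.1 / 3.7 |

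**Generality of the 0.5 gap.** With x = 1/RR and RR below 0.5, E(x/2) = ½[x + √(x(x − 2))], which is less than ½[x + √(x(x − 1))] = ½E(x). Changing the reference from 1 to 0.5 therefore always more than halves the point-estimate value.

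**Borderline success.** If the upper limit is just under 0.5, the estimate is about 0.33 (1 year) or 0.35 (3 years). The planned E-value would be 5.5 or 5.2. The limit against 1 gives 3.4, and the limit against 0.5 gives about 1.

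These limits ignore the variance added by weighting. A wider interval would lower the limit-based values.

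**The case against.** The formula is not wrong. The text defines its quantity as explaining away the whole association, and for that the reference is 1. Neither document presents the E-value as a measure of the robustness of the 0.5 decision. The section is exploratory, triggers no decision and is read with clinical input. The confidence interval will be reported, so a reader could compute the missing value. All of this stands and keeps the point modest. It does not remove the gap between estimate and limit.

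Two stronger readings are tempting.

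- **Robustness is overstated at least two-fold, without condition.** A reader might infer this from SAP 7.9.3 alone. The documents do not support it: protocol 10.1 says the tested nulls are not shifted, and then only the 1.5 to 1.6-fold gap remains. Protocol 10.1 and SAP 7.6 also describe the 0.5 margin as making the evidence more robust, and SAP 7.6 lists propensity methods alongside it to deal with non-randomised uncertainty. On that view, asking whether confounding could explain the entire benefit is a legitimate question in its own right.
- **A confounder weaker than the printed E-value would usually produce a false success.** A case can be constructed. Take a factor present in 20% of Roctavian and 60% of SoC participants that multiplies bleeding by 4. It turns a true ratio of 0.5 into 0.5 × (1 + 0.2 × 3)/(1 + 0.6 × 3) = 0.286, with a planned E-value of about 6.5. But these strengths are assumed, come from neither document, and would have to persist after propensity adjustment that always includes prior ABR. A true ratio of 0.5 is also a real halving of bleeds. This is an illustration, not an error rate for the study.

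SAP 7.10 also promises a quantitative bias assessment. It names no method, so it does not fill the gap.

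**Conclusion.** The point holds in a limited form. The planned E-value is correctly defined for a null of 1, but it omits the confidence limit and does not measure robustness of the conclusion drawn under SAP 7.9.3. Under either null, 6.5 compares with 4.1 to 4.4 for the limit against 1. The values 2.9 and 1.6 to 1.8 apply only if the 0.5 test governs, which the documents leave in conflict. All figures are expectations at the design rates, dispersion and group sizes, without weighting variance. The primary estimate, its interval and the success rule are unaffected. This is an inexpensive improvement to a figure that will inform interpretation.

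**What to change.** Make the same change in protocol 10.3.4 and SAP 7.8.2.2:

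1. State that the E-value is computed from the weighted rate ratio, not from the difference in mean ABR.
2. Report it against 1 for the point estimate and for the confidence limit nearest the null, with value 1 if the interval includes 1.
3. Wherever the 0.5 hypothesis is tested, also apply the formula to 0.5/RR and 0.5/upper limit, with value 1 if the quantity entered is not above 1 (for the limit, when it is 0.5 or higher).
4. Say beside each value which conclusion it concerns: any benefit, or a ratio below 0.5.
5. Reconcile protocol 10.1 and 10.3.6.1 with SAP 7.9.3 on the tested null and the primary measure, so that it is clear whether step 3 applies to the primary result.

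The cost is a few lines of text and simple arithmetic on output already planned, with no new data. The one downside is that the reported robustness figures will look less favourable.

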7.8.2.3. Baseline Comparison of Groups for Propensity Score Development

Participant characteristics will be presented for all baseline variables described in Table 3 and Table 4, along with tests for difference using appropriate statistical testing; Welch's t-test for continuous variables, and the Chi-square test for categorical variables.

SMD will be calculated for continuous and categorical variables. SMD represents the most commonly used statistic to examine the balance of covariate distribution between groups, with a value greater than 0.1 indicating some imbalance between groups and > 0.25 indicating poor imbalance, where the model should either be improved or rejected in favor of an alternative model.³³ If imbalance of > 0.25 remains, the propensity score model will be refined by adding additional covariates, adding interaction terms and/or conducting appropriate transformation of the covariates (squared, log, etc.). Any covariates that remain imbalanced (SMD>0.25) after further refinement of the propensity score model (due to lack of propensity score model convergence) will be removed from the propensity score model and included/adjusted for in the regression model (for model-based analyses – i.e., bleeding events) to estimate the ATE on the outcome.

After propensity score methods have been applied, tabulations will be repeated with p-values and SMDs re-calculated to investigate any meaningful differences remaining after propensity score-adjustment, both in the characteristics included in the propensity scoring, and also those not included. Although all baseline characteristics will be presented for completeness, the balance of the variables included within the propensity score models will be the focus due to the importance assigned to these characteristics.

In accordance with guidance that model-evaluation tools of the logistic regression are secondary to the balancing of participant characteristics,^{34, 35} additional analyses will also be performed with the omission of highly correlated variables. Collinearity among covariates that are used to generate weighting from the IPTW method will be assessed by the variance inflation factor (VIF) and

conditional index. A conditional index > 10 indicates that high collinearity exists among some of the covariates. VIF will also be checked to confirm collinearity, with VIF > 5 as moderate and VIF > 10 as high collinearity. If high collinearity is detected, an additional analysis will be conducted by dropping the covariate(s) that are responsible for the high collinearity until the conditional index for all covariates drops to 10 or below, and then recreate the weights and refit the IPTW model for the primary outcome. Clinical input will be solicited to select the variable to be retained in the model. In the event a decision cannot be reached using only clinical input, a statistical tiebreaker (Akaike Information Criterion [AIC]) will be used. The model will be run separately with each variable and the model resulting in the lower AIC will be selected. Results will be compared with those from models using weights generated from the full set of covariates to assess the robustness of the primary results.

